### General analysis conventions

**Pooling of centers:** Unless specified otherwise, data from all study centers will be pooled for the analysis. Due to expected small number of patients enrolled at centers, no center effect will be assessed.

**Categorical data** (e.g., gender, race, etc.) will be summarized by frequency and percentages by Cohort along with 95% Confidence interval (as appropriate); a missing category will be included as applicable. Percentages will be calculated using the number of patients in the relevant Cohort as the denominator. 95% Confidence Interval for the percentages will be evaluated using Clopper-pearson method.

**Continuous data** (e.g., age, body weight, etc.) will be summarized by appropriate descriptive statistics (i.e., mean, standard deviation, median, minimum, Q1, Q3, and maximum) by Cohort [REDACTED]

estimated rate by specific timepoints will be reported along with their respective 95% Confidence interval(s).

### 2.1.1 General definitions

#### Investigational drug and study medication

**Investigational drug** will refer to the ABL001 only. Whereas **study medication** will refer to ABL001 [asciminib (40 mg BID, 80 mg QD or 200 mg BID)]. Novartis is supplying asciminib to the investigational site as 20 mg and 40 mg tablets.

#### Treatment Cohorts

Patients without T315I mutation status are selected randomly between Cohort A (without T315I) and Cohort B (without T315I). Patients harboring the T315I mutation are allocated to Cohort C.

Without T315I mutation		With T315I mutation
Cohort A	Cohort B	Cohort C
40 mg BID	80 mg QD	200 mg BID

#### Date of first administration of study medication

The date of first administration of study medication is derived as the first date when a non-zero dose of study medication was administered as per the Dosage Administration Record (DAR) electronic case report form (eCRF). The date of first administration of study medication will also be referred as **start of study medication**.

The date of first administration of study medication is the same as the date of first administration of investigational drug.

#### Date of last administration of study medication

The date of last administration of study medication is defined as the last date when a non-zero dose of study medication was administered as per the DAR eCRF.

The date of last administration of study medication is the same as the date of last administration of investigational drug.

#### Study day

The study day describes the day of the event or assessment date, relative to the reference start date.

- The date of the event (visit date, onset date of an event, assessment date, etc.) – reference start date + 1 if event is on or after the reference start date;
- The date of the event (visit date, onset date of an event, assessment date, etc.) – reference start date if event precedes the reference start date.

The reference start date for safety assessments (e.g., adverse event onset, laboratory abnormality occurrence, vital sign measurement, dose interruption, [REDACTED] etc.) is the start of study medication.

The reference start date for all other, non-safety assessments (e.g., molecular response, survival time, disease progression, ECOG performance status, [REDACTED] etc.) is the date of random allocation of patient to their respective Cohort.

The study day will be displayed in the data listings. If an event starts before the reference start date, the study day displayed on the listing will be negative.

For “time since event” data (e.g., medical history), the duration (in days) will be calculated as treatment start date-diagnosis date.

### Baseline

For safety & efficacy evaluations, the last available assessment on or before the date of start of study medication of asciminib (40 mg BID, 80 mg QD & 200 mg BID) is taken as “baseline” assessment. For pre-dose electrocardiogram (ECG), the last available assessment before the treatment start date/time is used for baseline.

For ECGs, where study requires multiple replicates per time point, the average of these measurements would be calculated for baseline (if not already available in the database).

In rare cases where multiple laboratory measurements meet the baseline definition, with no further flag or label that can identify the chronological order, then the following rule should be applied: If values are from central and local laboratories, the value from central assessment should be considered as baseline.

If patients have no value as defined above, the baseline result will be missing.

### On-treatment assessment/event and observation periods

For adverse event, reporting the overall observation period will be divided into two mutually exclusive segments:

- **Pre-treatment period:** from day of patient's informed consent to the day before first administration of study medication
- **On-treatment period:** from date of first administration of study medication to 30 days after date of last actual administration of any study medication (including start and stop date).

**Note:** Patients will be treated for up to LPFT + 72 weeks. This will be the last actual administration of study medication for each patient if the patient has not discontinued study medication earlier. After this period, the assigned study medication will be made available, may be outside of this study, to patients who in the opinion of the investigators are still deriving clinical benefit.

### Visit window

#### Windows for multiple assessments

In order, to summarize molecular response, Hematologic Response, [REDACTED] collected over time (including unscheduled visits), the assessments will be time slotted. The following general rule will be applied in creating the assessment windows: If more than one assessment is done within the same time window, the assessment performed closest to the target date will be used. If two assessments within a time window are equidistant from the target date, then the average of the two assessments will be used. If multiple assessments on the same date, then the average will be used. Data from all assessments (scheduled and unscheduled), including multiple assessments, will be listed.

**Table 2-1 Time windows for molecular response (BCR-ABL1 quantification by RQ-PCR)**

Assessment	Target day of assessment	Time Interval
Baseline	≤ 1	≤ Day 1#
Week 4	29	Day 2 to day 57
Week 12	85	Day 58 to day 127
Week 24	169	Day 128 to day 211
Week 36	253	Day 212 to day 295
Week 48	337	Day 296 to day 421
Week 72	505	Day 422 to day 589

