8.1.4 Visit Windows

Study visits from Week 1 Day 1 to Week 2 Day 1 should be completed on the designated date [with an allowed “visit window” of +/- 2 day for Week 1 Day 1 and Week 2 Day 1]. All visits up until Week 4 day 1 need to be performed live by the treating physician on the site.

Study visits from Week 4 to Week 72 (EOT) should be completed every 4 weeks on the designated date [with an allowed “visit window” of +/- 7 days]. After Week 4 day 1, remote visits can be performed using tele-medicine approach with the exception of visits on Weeks 12, 24, 36, 48 and 72.

A delayed visit will have no impact on the next planned visit. The next visit should be completed as scheduled in order to avoid accumulation of additional weeks.

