| | No sample collected - testing is performed on the "Blood for BCR-ABL1 quantification by RQ-PCR" sample | Upon confirmed loss of MMR and/or End of Treatment | Anytime |

β = only applicable if the visit is in-person

During the study, peripheral blood samples will be collected into PAXgene™ Blood RNA tubes for all RQ-PCR assessments. Detailed instructions for the collection, handling, and shipment of RQ-PCR and mutation samples are outlined in the [\[CABL001AUS04 Laboratory Manual\]](#).

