# Day 1 = Date of random allocation of patients

[figure not shown]
EOT assessments are mapped to the time points as needed.

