#### **Rate of CHR, MR2, MMR, by 12, 24, 48, 72 weeks of therapy and Rate of MR4 & MR4.5 by 24, 48, 72 weeks of therapy**

- The rate of **Complete Hematologic Response (CHR)** by 12, 24, 48 and 72 weeks. **CHR** is defined as all of the following present for  $\geq 4$  weeks:
  - WBC count  $< 10 \times 10^9/L$
  - Platelet count  $< 450 \times 10^9/L$
  - Basophils  $< 5\%$
  - No blasts and promyelocytes in peripheral blood
  - Myelocytes + metamyelocytes  $< 5\%$  in peripheral blood
  - No evidence of extramedullary disease, including spleen and liver
- The rate of **molecular response (MR2)** by 12, 24, 48 and 72 weeks after the start of first study medication. **MR2** is defined as  $\geq 2$  log reduction of BCR-ABL transcript from standardized baseline or  $\leq 1\%$  BCR-ABL/ABL % by international scale, measured by real-time quantitative PCR (RQ-PCR).

- The rate of **major molecular response (MMR)** by 12, 24, 48 and 72 weeks after the start of first study medication. MMR is defined as  $\geq 3$  log reduction of BCR-ABL transcript from standardized baseline or  $\leq 0.1\%$  BCR-ABL/ABL % by international scale, measured by real-time quantitative PCR (RQ-PCR).
- The rate of **molecular response (MR4)** by 24, 48 and 72 weeks after the start of first study medication. **MR4** is defined as  $\geq 4$  log reduction of BCR-ABL transcript from standardized baseline or  $\leq 0.01\%$  BCR-ABL/ABL % by international scale, measured by real-time quantitative PCR (RQ-PCR).
- The rate of the **molecular response (MR4.5)** by 24, 48 and 72 weeks after the start of first study medication. **MR4.5** is defined as  $\geq 4.5$  log reduction of BCR-ABL transcript from standardized baseline or  $\leq 0.0032\%$  BCR-ABL/ABL % by international scale, measured by real-time quantitative PCR (RQ-PCR).

For rate of MR2, MMR, MR4, MR4.5 by any pre-specified time point patients will be considered as responder if he/she achieves the particular response at least once by the specific timepoint. If patient discontinuing the treatment prior to a specific time point due to any reason and not achieved the particular response before the discontinuation will be considered as non-responder.

For each time point, the proportion of patients achieving the specific response levels will be presented together with an exact 95% Clopper-Pearson confidence interval by cohort. The rates over time will be displayed graphically using the Bar Charts with 95% C.I. as whiskers.

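### SAP Table 2-1 gives the protocol's Week 60 PCR sample no window of its own, and its use in the 48- and 72-week response rates is left unsettled

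*SAP*

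**What the plan says.** Protocol Tables 8-1 and 8-3 schedule a blood sample for BCR-ABL1 quantification at Week 60, with the footnote "only applicable if the visit is in-person". Week 60 may be held remotely: Protocol 8.1.4 allows tele-medicine after Week 4 "with the exception of visits on Weeks 12, 24, 36, 48 and 72". The permitted visit window from Week 4 onward is 7 days either side.

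SAP Table 2-1 has rows for Weeks 4, 12, 24, 36, 48 and 72 only. Week 48 (target Day 337) covers "Day 296 to day 421" and Week 72 (target Day 505) covers "Day 422 to day 589". The footnote reads "Day 1 = Date of random allocation of patients". For several samples in one window, the SAP says: "If more than one assessment is done within the same time window, the assessment performed closest to the target date will be used".

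For the MR2, MMR, MR4 and MR4.5 rates, SAP 2.8.2 counts a patient as a responder if "he/she achieves the particular response at least once by the specific timepoint", with time measured from the start of study medication. It does not say whether a time point ends at its target day, at the actual visit or at the upper limit of its window.

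**The concern.** A scheduled PCR sample has no analysis window, and the boundary between the two neighbouring windows sits on that sample's own target day. Under the slotting rule, moving a compliant visit by one day can change its label from Week 48 to Week 72.

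Two programmers could then build the response rates differently, each with support in the text:

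- **Window-limit reading.** Every sample up to the end of the Week 48 window counts towards the by-Week-48 rate. A response first found some 12 weeks after the Week 48 target is then a 48-week response if the sample fell on Day 414 to 421, and is not if it fell on Day 422 or later.
- **Slotted-value reading.** Only the closest-to-target value in each window counts. The Week 60 sample is dropped whenever a nearer one exists, and stands in for Week 48 when the Week 48 sample is missing. A response seen only at Week 60 could then be absent from the by-Week-72 rate.

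At stake are the 48-week rates and, under the second reading, the 72-week rates. Only patients seen in person at Week 60 are affected.

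**Working it through.** **Inputs.** Targets and limits: SAP Table 2-1. Visit window of ±7 days: Protocol 8.1.4 and the notes to Table 8-1. Week 60 sample: Protocol Table 8-3. Cohort size of 45: Protocol 12.9.

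**1. Reproduce the SAP table.** Target day = 7 × week + 1 gives 29, 85, 169, 253, 337 and 505, all as printed. Upper limit = midpoint of adjacent targets gives 57, 127, 211, 295 and (337 + 505)/2 = 421, all as printed. Day 421 therefore follows from the SAP's own rule once Week 60 is left out.

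**2. Place Week 60 on the same scale.** 7 × 60 + 1 = 421, the last day of the Week 48 window and (421 − 337)/7 = 12 weeks past the Week 48 target.

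**3. Count permitted days on each side.** Let k be the days from allocation to first dose. A compliant Week 60 visit falls on Day 414 + k to 428 + k. The number of those 15 days at or before Day 421 is 8 − k for k up to 7, then 0.

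| Lag k (days) | Slotted to Week 48 | Slotted to Week 72 |
|---|---|---|
| 0 | 8/15 | 7/15 |
| 1 | 7/15 | 8/15 |
| 5 | 3/15 | 12/15 |
| 7 | 1/15 | 14/15 |
| 8 or more | 0/15 | 15/15 |

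The lag is not given in the documents. Protocol Table 8-1 places cohort assignment in the screening column (Day −21 to −1), so 0 to 21 days is taken as the range.

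**4. Closest-to-target rule (k = 0).** A compliant Week 48 sample lies at most 7 days from Day 337. A Week 60 sample in that window lies at least 414 − 337 = 77 days away. On the other side, the smallest distance to Day 505 is 505 − 428 = 77 days. The Week 60 value therefore fills either slot only when no nearer sample exists.

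**5. Size under the window-limit reading.** Shift in the by-Week-48 rate = (share slotted to Week 48) × (share of patients first responding at Week 60). The second factor is an assumption, 5% to 15%. With k = 0, every Week 60 visit in person and visit days uniform:

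- 5%: 8/15 × 5 = 2.7 points, or 1.2 of 45 patients
- 10%: 8/15 × 10 = 5.3 points, or 2.4 of 45
- 15%: 8/15 × 15 = 8.0 points, or 3.6 of 45

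With k = 5 and 5%, the shift is 3/15 × 5 = 1.0 point. With k of 8 or more it is 0.

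**6. Comparison with Kaplan-Meier.** SAP 2.8.2 also plans cumulative incidence at 48 weeks from first dose to first documented response. A response dated about 60 weeks is not in that estimate, but can be in the by-Week-48 proportion under the window-limit reading.

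**The case against.** The case on the other side is substantial.

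- **The rate definition is anchored to first dose.** Read literally, a rate by 48 weeks after the start of study medication excludes a 60-week sample. No sentence ties the rate to the window limit; the windows are introduced for summaries over time. This stands, so the window-limit reading is a possibility that the SAP leaves open, not its stated rule.
- **The closest-to-target rule protects the by-visit summary.** This stands whenever the Week 48 sample, a mandatory on-site visit, was taken. It also creates the second problem: the Week 60 result is discarded.
- **Day 1 is allocation.** The 8-of-15 split needs allocation and first dose on the same day. This stands, and it makes the label depend on an administrative interval as well.
- **The gain between Weeks 48 and 60 may be small.** Protocol 1.1.2.2 reports MMR rising from 37% to 48% between 6 and 12 months without T315I, and from 25% to 28% with it. Pro rata over 12 of 26 weeks (an assumption) this is 11 × 12/26 = 5.1 points and 3 × 12/26 = 1.4 points: the bottom of the assumed range, and below it for Cohort C. This stands; 8 points is a ceiling.
- **Week 60 was removed on purpose, and no endpoint is defined there.** The document history confirms the removal. The protocol still collects the sample, however, and the SAP gives no rule for it.

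A reader might infer that Week 60 samples are routinely credited to Week 48 by chance and raise the 48-week rate by about 5 points, or that Day 421 is an arithmetic slip. The documents support neither. The first needs the window-limit reading, zero lag, full in-person attendance and 10% first responders together. The second fails because Day 421 is the correct midpoint of the two remaining targets.

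**Conclusion.** The gap is real and modest. The protocol collects a sample for which the SAP has no window, and the slotting rule labels it Week 48 or Week 72 on a one-day difference, or discards it. The SAP does not settle which samples feed the by-Week-48 and by-Week-72 rates.

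The possible effect on the by-Week-48 rate runs from 0 to about 8 percentage points. The upper end rests on the window-limit reading, no lag between allocation and dosing, all Week 60 visits in person, uniform visit days and 15% of patients first responding at Week 60. Under the slotted-value reading there is no such inflation unless the Week 48 sample is missing, but a response seen only at Week 60 can be lost from the 72-week rate. If all samples to the end of the Week 72 window count, that rate is unaffected. Kaplan-Meier time to response uses documented dates and should not be affected by the slotting.

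The endpoints are secondary and descriptive, with no hypothesis test, and the primary safety analysis is untouched. The point still merits a correction because it is cheap and removes an avoidable choice at programming.

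**What to change.** Restore the Week 60 row in SAP Table 2-1 under the SAP's own midpoint rule, with midpoints (337 + 421)/2 = 379 and (421 + 505)/2 = 463:

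| Assessment | Target day | Interval |
|---|---|---|
| Week 48 | 337 | Day 296 to 379 |
| Week 60 | 421 | Day 380 to 463 |
| Week 72 | 505 | Day 464 to 589 |

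Add two sentences:

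1. The by-Week-48 rate uses all assessments up to the end of the Week 48 window (Day 379), and the by-Week-72 rate uses all assessments up to the end of the Week 72 window, including Week 60.
2. Day 1 for these windows is the date of first dose, in line with the rate definition in SAP 2.8.2; this replaces the allocation footnote.

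With days counted from first dose, compliant Week 48 visits fall on Day 330 to 344 and Week 60 visits on Day 414 to 428, so no scheduled sample lies near the new limit. Even if Day 1 stayed at allocation, a compliant Week 60 visit would remain in its own window for lags up to 463 − 428 = 35 days.

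The cost is three table rows and two sentences, with no new data.

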# Day 1 = Date of random allocation of patients

[figure not shown]
EOT assessments are mapped to the time points as needed.

**Table 2-2 Time windows for Hematologic response assessment**

Assessment	Target day of assessment	Time Interval
Week 12	85	Day 2 to day 127
Week 24	169	Day 128 to day 211
Week 36	253	Day 212 to day 295
Week 48	337	Day 296 to day 421
Week 72	505	Day 422 to day 589

# Day 1 = Date of random allocation of patients

EOT assessments are mapped to the time points as needed.

### Last contact date

The last contact date will be derived for patients not known to have died at the respective analysis data cut-off date using the last complete date among the following:

**Table 2-5 Last contact date data sources**

Source data	Conditions
Date of random allocation	No condition
Last contact date/last date patient was known to be alive from Survival Follow-up page	Patient status is reported to be alive, lost to follow-up or unknown
Start/End dates from further antineoplastic therapy	Non-missing medication/procedure term
Start/End dates from drug administration record	Non-missing dose. Doses of 0 are allowed
End of treatment date from end of treatment page	No condition
Any specific efficacy (molecular or cytogenetic) assessment date if available	Evaluation is marked as 'done'
Laboratory/█ collection dates	Sample collection marked as 'done'
Vital signs date	At least one non-missing parameter value
Performance status date	Non-missing performance status
Start/End dates of AE	Non-missing verbatim term

The last contact date is defined as the latest complete date from the above list on or before the respective data cut-off date. The cut-off date will not be used for last contact date unless the patient was seen or contacted on that date. No date post cut-off date will be used. Completely imputed dates (e.g., the analysis data cut-off date programmatically imputed to replace the missing end date of a dose administration record) will not be used to derive the last contact date.

The last contact date will be used for censoring of patients in the analysis of overall survival.

## 2.2 Analysis sets

### Full Analysis Set (FAS)

The Full Analysis Set (FAS) comprises all patients to whom study medication has been assigned. According to the intent to treat principle, patients will be analyzed according to the study medication and Cohort they have been assigned.

All the secondary efficacy endpoints will be analyzed using FAS.

### Safety Set (SS)

The Safety Set (SS) includes all patients who received at least one dose of study medication. Patients will be analyzed according to the study medication (regimen) they actually received.

The primary and all safety endpoints analysis will be performed on Safety Set.

[REDACTED]

### Patient Classification

Patients may be excluded from the analysis populations defined above based on the protocol deviations entered in the database and/or on specific patient classification.

During the study, major and minor protocol deviations will be identified and collected on an ongoing basis as they occur. Refer to special data handling in data management documents. The decision whether patients will be included or excluded in the appropriate analysis sets will be determined based on the severity levels of the PDs.

#### 2.2.1 Subgroup analyses

Subgroup analyses will be performed based on the patient's baseline status:

- Age: (< 65 years; ≥ 65 years)
- Patients with resistance: (BCR-ABL ratio at baseline >10%)
- Previous treatment with Ponatinib (Yes or No)
- By number of prior TKI therapies: 2, 3, ≥4

Summary tables and figures will be generated only for subgroups with at least 5% of the total sample size of full analyses set (for efficacy endpoint) or safety set (for safety endpoint).

All primary and secondary endpoints will be analyzed and summarized within each subgroup. Additionally, as the study is ongoing during COVID-19 pandemic, to address the impact of COVID-19 (if any) AEs, SAEs, Abnormal lab findings and notable vital signs will be summarized and reported if COVID-19 infected patient count exceeds 5% of the total sample size of safety set.

As appropriate, given the significance of the impact of COVID-19 on the enrolled patients, a sensitivity analysis may be performed on the safety and efficacy data evaluating the impact of COVID-19 on the study, if COVID-19 infected patient count exceeds 5% of the total sample size.

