| Purpose and rationale | 
Asciminib (ABL001) is a potent BCR-ABL1 allosteric inhibitor currently being developed by Novartis for the treatment of CML (Chronic Myelogenous Leukemia). Unlike drugs such as imatinib, nilotinib, dasatinib, bosutinib and ponatinib, which bind to the ATP-site of the ABL kinase domain, asciminib binds to the myristoyl pocket and consequently, restores the negative regulation of the kinase activity¹. Given this unique mechanism of action, it has been proven to have activity against BCR-ABL1 mutations that are known to confer resistance to the ATP site TKIs (tyrosine kinase inhibitors)¹. Moreover, the selective binding of asciminib is predicted to reduce toxicities, which is an encouraging feature for patients where side effects from previous treatments were the reason for drug discontinuation.
 
Based on phase I data, asciminib has been proven safe and effective in patients who had more than 2 lines of therapy, with 32% and 44% of those achieving MMR in 6 and 12 months, respectively². The incidence of grade 3/4 treatment emergent AEs were mostly less than 10%, which implies a favorable safety profile in a heavily pre-treated CML population.
 
The ongoing ASCEMBL study is a phase III study, which is investigating the efficacy of treatment with asciminib versus bosutinib in CML-CP patients with at least 2 prior TKI therapies. Data from this study are expected to be presented at an upcoming medical meeting and results will be shared with regulatory authorities.
 
Despite its phase III design with randomization, questions remain such as safety and efficacy on a larger patient population including those harboring the T315I mutation and of a daily dosing schedule. A once daily regimen could be more convenient as we believe it will greatly improve patient's adherence as well as quality of life. For that dosing schedule, the dose of 80 mg was selected based on similar efficacy and safety profile when compared to 40 mg twice daily from early phase data.
 
The study currently proposed is a phase IIIb open-label study on patients with resistant or intolerant CML-CP previously treated with at least 2 prior TKIs in the absence of T315I mutation and at least 1 prior TKI in the presence of the T315I mutation. Our goal is to gain further efficacy and safety data with asciminib monotherapy on a larger population of patients.
 
The study will contain the following cohorts:
 
 • Cohort A asciminib 40 mg BID • Cohort B asciminib 80 mg QD • Cohort C asciminib 200 mg BID, exclusively for those harboring the T315I mutation |

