Please refer to (Hughes, 2019) and the latest [Asciminib Investigator's Brochure] for more details.

Safety:

Asciminib was generally well tolerated in heavily pre-treated CML patients resistant to or intolerant of prior TKIs. As of March 2020, 239 patients were evaluable for safety. Seventy six study discontinuations have been reported; the most frequent reason for discontinuation was progressive disease, reported in 38 patients (15.9%). Adverse events leading to treatment discontinuation were reported in 15 patients (6.3%). Death leading to treatment discontinuation was reported in 3 patients (1.3%) (one patient in asciminib 20 mg BID due to aspiration pneumonia after bypass procedure and two patients with ALL with 80 mg and 160 mg BID due to progressive disease).

Among the 150 patients treated with asciminib monotherapy, almost all (94.7%) patients reported at least one AE, including 49.3% reported grade 3/4 AEs. The most common AEs (> 10%) among patients treated with 40 mg BID (n=35), regardless of study drug-relationship, were increased lipase, fatigue, diarrhea, thrombocytopenia, neutropenia, arthralgia, rash, headache, increased amylase, nausea, vomiting, abdominal pain, pyrexia, upper respiratory tract infection, back pain, hypertension, cough, pruritus, pain in extremity, dyspnea, bone pain, peripheral oedema, non-cardiac chest pain and insomnia. The most common reported grade 3/4 event was increased lipase (17.1%).

Forty-seven of 150 patients with CML-CP or CML-AP treated with asciminib single agent (31.3%) were reported with serious adverse events (SAE).

Electrocardiogram (ECG) data shows no reported QT prolongation (increase > 60 msec or new > 500 msec) in 40 mg BID asciminib monotherapy group. There were no reports of QT prolongation (increase > 60 msec) and two reports of new >500 msec (one each in 80 mg QD and 120 mg QD) among all asciminib monotherapy group.

Please refer to the latest [Asciminib Investigator's Brochure] for more details.

Pharmacokinetics:

PK data from 190 patients were available from the [CABL001X2101] study, as of 01-Sep-2017. When given as a single agent on a twice daily schedule, patients received escalating doses of asciminib ranging from 10 to 200 mg.

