1.2 Purpose

Thanks to the advances in CML treatments, many of these patients can now have life expectancy similar to the general population. However, there is a significant proportion of patients who unfortunately experience treatment failure due to either resistance or intolerance. When considering patients treated with frontline imatinib, 31% exhibit treatment failure and progress to second-line treatment; of those, half of them progress to third-line treatment (Akard, 2013). On patients starting treatment with 2nd generation TKI (2G-TKI), treatment failure rate is at 13% and when they move on to second-line treatment, around 60% of them exhibit disease progression and move on to third-line treatment.

[figure not shown]
Given the poor outcomes of patients that progress after successive lines of therapy, there remains an unmet need for new compounds that can provide CML patients optimal disease management. It is worthwhile mentioning the lack of defined treatments recommendations once patients move on to second-line treatment and beyond. NCCN guidelines recommend treating patients with any of the 2G-TKIs if imatinib was given as the frontline agent; if 2G-TKI was used for first-line treatment, any 2G-TKI can be considered for subsequent treatment, although some experts advocate for ponatinib if the reason for treatment discontinuation was related to resistance (Hochhaus, 2020).

In addition, patients harboring T315I mutation have few treatment choices since this mutation confers resistance to all TKIs with the exception of Ponatinib. Unfortunately, Ponatinib is associated with high risk of cardiovascular complications and many of these patients are then not eligible for treatment. Based on data from ongoing study [CABL001X2101], 53.8% of CML-CP patients with this mutation who had not been previously treated with Ponatinib were able to achieve MMR by 6 months (Hughes, 2020). Therefore, asciminib represents a promising agent for this CML-patient population that the current study is attempting to address.

2 Objectives and endpoints

| Table 2-1 | Objective(s) | Endpoint(s) |
|-----------|--|--|
| | Primary Objective(s) | Endpoint(s) for primary objective(s) |
| | 
 To evaluate safety profile of monotherapy asciminib in CML-CP in 3L and beyond, for Cohorts A and B | 
 AEs, SAEs and laboratory evaluation for 24 Weeks. |
| | Secondary Objective(s) | Endpoint(s) for secondary objective(s) |

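### The resistance subgroup in SAP 2.2.1 is really a baseline BCR-ABL cut, and the prior-TKI categories omit Cohort C patients with one prior TKI

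*SAP*

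**What the plan says.** Protocol 12.4.3 lists subgroups by baseline status, including patients with resistance and number of prior TKI therapies. It defines neither and asks only for summaries within each subgroup.

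SAP 2.2.1 makes both operational. The first becomes "Patients with resistance: (BCR-ABL ratio at baseline >10" per cent and the second becomes "By number of prior TKI therapies: 2, 3, ≥4". The SAP applies its subgroups to every primary and secondary endpoint, subject to a display rule: "Summary tables and figures will be generated only for subgroups with at least 5% of the total sample size" of the relevant analysis set. SAP 2.1.1 defines baseline as "the last available assessment on or before the date of start of study medication of asciminib". SAP section 4 declares no departure from the protocol's analyses.

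The protocol's own use of the word resistance is consistent:

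- Protocol summary, purpose and rationale: "patients with resistant or intolerant CML-CP previously treated with at least 2 prior TKIs"
- Section 1.2: patients who "experience treatment failure due to either resistance or intolerance"
- Section 1.1.2.2: "heavily pre-treated CML patients resistant to or intolerant of prior TKIs"
- Section 1.2, on T315I: "this mutation confers resistance to all TKIs with the exception of Ponatinib"

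In section 5.1, criterion 6 requires failure of, or intolerance to, the most recent TKI. Criterion 5 requires two prior TKIs without T315I but only one with it.

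**The concern.** A reader of a resistance table will take it to describe patients whose earlier TKIs stopped working, as opposed to those who could not tolerate them. A cut on the last value before asciminib describes something else, namely how much disease the patient carried at the start. Because the subgroups apply to all endpoints, every such table would carry the wrong label. The documents show no other table that separates failure from intolerance, although parts of the SAP are redacted.

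The second problem is simpler. The prior-TKI categories start at 2, while Cohort C can include patients with one prior TKI. The subgroup counts for that cohort need not add up to the cohort total.

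**Working it through.** **Part 1: what the 10% rule captures.** Criterion 6 in protocol 5.1 is the only place where the protocol defines failure of, or intolerance to, prior TKI therapy. Its failure criteria, set against the SAP rule:

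| Failure criterion (most recent TKI) | Needs a ratio above 10%? |
|---|---|
| Month 3, confirmed | Yes, at month 3 of that TKI |
| Month 6 | Yes, at month 6 of that TKI |
| Month 12, ratio above 1% | No |
| Any time, loss of CHR or MR2 | No |
| Any time, new potentially resistant mutation | No |
| Beyond 12 months, ratio of 1% or more, or loss of MMR | No |
| Any time, new clonal abnormality in Ph+ cells | No |

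Two of the seven use 10% and five can be met at or below it. The two 12-month criteria largely overlap; counted as one, the tally is four of six. Even the two 10% criteria refer to fixed times on the previous drug, not to asciminib baseline. Intolerance carries no transcript limit. The separate list for failure on asciminib (protocol 9.1.1) has six criteria, of which one uses 10%, from week 24 on.

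Three patients run through the SAP rule:

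- Ratio 5% after 18 months on the last TKI. 5% ≥ 1%, so criterion 6 failure is met; 5% is not above 10%, so the patient is left out of the resistance subgroup.
- T315I present, ratio at or below 10%, last TKI not ponatinib. The protocol calls this mutation resistant to that drug; the patient is left out.
- Last TKI stopped for toxicity before month 3, ratio above 10% when asciminib starts, no failure criterion met. The patient is counted as resistant.

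The label matters when response rates are read. MR2 is ≤1% and MMR is ≤0.1% on the international scale (SAP Table 5-3). From 10%, the fall needed is log10(10/1) = 1 log for MR2 and log10(10/0.1) = 2 logs for MMR, so patients above 10% need more than that. From 5% it is log10(5/1) = 0.70 and log10(5/0.1) = 1.70 logs. A lower response rate above 10% would therefore partly reflect starting level. SAP 2.8.2 excludes patients already in molecular response at baseline from the time-to-event analyses only; it states no such exclusion for the rates.

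**Part 2: the prior-TKI categories.** Planned sizes are 45 + 45 + 25 = 115. In Cohorts A and B at least two prior TKIs are required, so 2, 3, ≥4 covers everyone. In Cohort C a patient with one prior TKI fits no category. The documents do not give that count; it lies between 0 and 25, and 25/115 = 21.7%. The same ceiling applies to T315I patients at or below 10% in part 1.

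**Would a one-TKI group be displayed?** The smallest n with n/N ≥ 5%:

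| Analysis set N | 0.05 × N | n needed |
|---|---|---|
| 100 | 5.00 | 5 |
| 101 | 5.05 | 6 |
| 115 | 5.75 | 6 |
| 120 | 6.00 | 6 |
| 121 | 6.05 | 7 |

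At the planned total, 6 of the 25 Cohort C patients (24%) would have to have had exactly one prior TKI.

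**The case against.** The best defence is that the SAP contradicts no definition. Protocol 12.4.3 leaves the term open, protocol section 12 leaves detailed methods to the SAP, and the SAP supplies a reproducible rule printed beside the label. The 10% figure is itself a protocol failure threshold. Criterion 6 speaks of failure rather than resistance, and protocol 1.2 uses treatment failure as the umbrella over both resistance and intolerance. A patient who stopped the last TKI for toxicity may also have been resistant to an earlier one.

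Much of this is fair. The SAP fills a gap, equating resistance with criterion 6 failure is an inference, and the third example shows misclassification only with respect to the last TKI. But the first two examples do not depend on that point, and no passage in the protocol uses resistance to mean transcript level at asciminib start. An open term does not license a rule that measures something else under the same name.

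It can also be said that T315I patients are visible as Cohort C in any case, that the prior-TKI gap does not touch the primary objective in Cohorts A and B, and that the 5% rule might suppress a one-TKI table anyway. These points limit the consequence, but the categories remain incomplete. Prior regimens are described by cohort (SAP 2.4.2), which does not supply endpoint results for the missing patients.

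Finally, redefining a subgroup late in an open-label study is post hoc. That stands, and it is why the change should be documented.

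**Conclusion.** Both parts hold. Followed as written, the plan would produce tables labelled resistance that show baseline disease burden, and a prior-TKI breakdown that is not exhaustive for Cohort C. The consequence is confined to descriptive subgroup tables: no hypothesis is tested, cohort-level estimates are unchanged, and the prior-TKI gap lies outside the primary objective. The number mislabelled by the 10% rule cannot be derived from the documents. The prior-TKI gap is 0 to 25 of about 115 (0 to 21.7%).

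Part 1 rests on reading resistance as the protocol pairs it, against intolerance. Part 2 rests on the subgroups covering Cohort C; the SAP applies them to all secondary endpoints, and nothing printed restricts them to Cohorts A and B. The change should be made.

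**What to change.** 1. Rename the first subgroup as baseline BCR-ABL level and show ≤10% against >10%.
2. Add a subgroup for resistance (failure of the last TKI) against intolerance under criterion 6, but only if it can be derived from data already collected. State how patients meeting both are classed.
3. If it cannot be derived, say in SAP section 4 that baseline BCR-ABL level replaces the protocol-listed resistance subgroup.
4. Use prior-TKI categories 1, 2, 3, ≥4. Apply the existing 5% rule to the actual FAS or Safety Set, and merge to ≤2, 3, ≥4 if the one-TKI group falls below it.

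The cost is SAP wording and subgroup flags. Baseline BCR-ABL and prior TKI therapy are in the assessment schedule (protocol Table 8-1), so items 1 and 4 need no new data. The documents do not show failure versus intolerance as a database field, which is why item 2 is conditional.

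The drawback is timing. SAP Amendment 1 preceded the primary-analysis lock, and Amendment 2 (15-Feb-2024) preceded a later interim lock, so primary subgroup tables may already exist. If they do, the change should be dated and explained, and those tables re-run for consistency.
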